7.1.1.2 CAEPR for GSK2141795

Comprehensive Adverse Events and Potential Risks list (CAEPR) for GSK2141795 (NSC 767034)

The Comprehensive Adverse Event and Potential Risks list (CAEPR) provides a single list of reported and/or potential adverse events (AE) associated with an agent using a uniform presentation of events by body system. In addition to the comprehensive list, a subset, the Specific Protocol Exceptions to Expedited Reporting (SPEER), appears in a separate column and is identified with bold and italicized text. This subset of AEs (SPEER) is a list of events that are protocol specific exceptions to expedited reporting to NCI via CTEP-AERS (except as noted [below](#)). Refer to the 'CTEP, NCI Guidelines: Adverse Event Reporting Requirements'

http://ctep.cancer.gov/protocolDevelopment/electronic_applications/docs/aeguidelines.pdf for further clarification.

Frequency is provided based on 150 patients. [Below](#) is the CAEPR for GSK2141795.

NOTE: Report AEs on the SPEER **ONLY IF** they exceed the grade noted in parentheses next to the AE in the SPEER. If this CAEPR is part of a combination protocol using multiple investigational agents and has an AE

listed on different SPEERs, use the lower of the grades to determine if expedited reporting is required.

Version 2.1, July 26, 2013¹

Adverse Events with Possible Relationship to GSK2141795 (CTCAE 4.0 Term) [n= 150]			Specific Protocol Exceptions to Expedited Reporting (SPEER)
Likely (>20%)	Less Likely (<=20%)	Rare but Serious (<3%)	
GASTROINTESTINAL DISORDERS			
Diarrhea			Diarrhea (Gr 2)
	Esophagitis		
	Gastrointestinal mucositis ²		
Nausea			Nausea (Gr 2)
Vomiting			Vomiting (Gr 2)
GENERAL DISORDERS AND ADMINISTRATION SITE CONDITIONS			
Fatigue			Fatigue (Gr 2)
METABOLISM AND NUTRITION DISORDERS			
Anorexia			Anorexia (Gr 2)
	Hyperglycemia		Hyperglycemia (Gr 2)
	Hypoglycemia		
RESPIRATORY, THORACIC AND MEDIASTINAL DISORDERS			
	Respiratory mucositis ³		
SKIN AND SUBCUTANEOUS TISSUE DISORDERS			
	Rash maculo-papular		

¹This table will be updated as the toxicity profile of the agent is revised. Updates will be distributed to all Principal Investigators at the time of revision. The current version can be obtained by contacting [contact]. Your name, the name of the investigator, the protocol and the agent should be included in the e-mail.

²Gastrointestinal mucositis may include Anal mucositis, Mucositis oral, Rectal mucositis, or Small intestinal mucositis under the GASTROINTESTINAL DISORDERS SOC.

³Respiratory mucositis may include Laryngeal mucositis, Pharyngeal mucositis, or Tracheal mucositis under the RESPIRATORY, THORACIC AND MEDIASTINAL DISORDERS SOC

Also reported on GSK2141795 trials but with the relationship to GSK2141795 still undetermined:

BLOOD AND LYMPHATIC SYSTEM DISORDERS - Leukocytosis

CARDIAC DISORDERS - Cardiac arrest, Left ventricular systolic dysfunction, Ventricular tachycardia

GENERAL DISORDERS AND ADMINISTRATION SITE CONDITIONS - Non-cardiac chest pain

HEPATOBIILIARY DISORDERS - Hepatic failure

INFECTIONS AND INFESTATIONS - Wound infection

INVESTIGATIONS - Alanine aminotransferase increased; Alkaline phosphatase increased; Aspartate aminotransferase increased; Ejection fraction decreased; GGT increased

METABOLISM AND NUTRITION DISORDERS - Hypokalemia; Hyponatremia, Hypophosphatemia

NERVOUS SYSTEM DISORDERS - Dysgeusia; Dysphasia

RENAL AND URINARY DISORDERS - Acute kidney injury
VASCULAR DISORDERS - Thromboembolic event

Note: GSK2141795 in combination with other agents could cause an exacerbation of any adverse event currently known to be caused by the other agent, or the combination may result in events never previously associated with either agent.

7.2 Adverse Event Characteristics

- **CTCAE term (AE description) and grade:** The descriptions and grading scales found in the revised NCI Common Terminology Criteria for Adverse Events (CTCAE) version 4.0 will be utilized for AE reporting. All appropriate treatment areas should have access to a copy of the CTCAE version 4.0. A copy of the CTCAE version 4.0 can be downloaded from the CTEP web site http://ctep.cancer.gov/protocolDevelopment/electronic_applications/ctc.htm.
- For expedited reporting purposes only:
 - AEs for the agent that are ***bold and italicized*** in the CAEPR (*i.e.*, those listed in the SPEER column, [Section 7.1.1](#)) should be reported through CTEP-AERS only if the grade is above the grade provided in the SPEER.
 - Other AEs for the protocol that do not require expedited reporting are outlined in [Section 7.3.4](#).
- **Attribution** of the AE:
 - Definite – The AE *is clearly related* to the study treatment.
 - Probable – The AE *is likely related* to the study treatment.
 - Possible – The AE *may be related* to the study treatment.
 - Unlikely – The AE *is doubtfully related* to the study treatment.
 - Unrelated – The AE *is clearly NOT related* to the study treatment.

7.3 Expedited Adverse Event Reporting

7.3.1 Expedited AE reporting for this study must use CTEP-AERS (CTEP Adverse Event Reporting System), accessed via the CTEP Web site (<http://ctep.cancer.gov>). The reporting procedures to be followed are presented in the “NCI Guidelines for Investigators: Adverse Event Reporting Requirements for DCTD (CTEP and CIP) and DCP INDs and IDEs” which can be downloaded from the CTEP Web site (<http://ctep.cancer.gov>). These requirements are briefly outlined in the tables below ([Section 7.3.3](#)).

In the rare occurrence when Internet connectivity is lost, a 24-hour notification is to be made to CTEP by telephone at [contact]. Once Internet connectivity is restored, the 24-hour notification phoned in must be entered electronically into CTEP-AERS by the original submitter at the site.

7.3.2 CTEP-AERS is programmed for automatic electronic distribution of reports to the following individuals: Study Coordinator of the Lead Organization, Principal Investigator, and the local treating physician. CTEP-AERS provides a copy feature for other e-mail recipients.

In addition to reporting to CTEP-AERS:

- Participating sites are responsible for submitting all reportable SAEs to their local IRB per institutional guidelines
- Participating sites are responsible for reporting all reportable SAEs to the MSK PI via e-mail within 3 calendar days of learning of the event. Participating sites should use the SAE Report Form found in MSK's internet-based Clinical Research Database, CRDBi-Multicenter, to report SAEs to MSK.
- Participating sites should notify the MSK PI of any grade 5 event immediately.

SAE contact information for the Coordinating Center is listed [below](#):

[name]
 Memorial Sloan Kettering Cancer Center
 [name]
 New York, NY 10065
 [contact]
 [contact]
 Email: [contact]

Multicenter Research Team
 Memorial Sloan Kettering Cancer Center
 Email: [contact]

The MSK Research Staff is responsible for submitting all SAEs to the MSK IRB/PB within 5 days of learning of the event.

Safety Reports:

- MSK will distribute outside safety reports to the participating sites immediately upon receipt.
- MSK must submit safety reports to the MSK IRB/PB according to institutional guidelines.
- Participating sites must submit safety reports to their institution's IRBs within 90 days of the date of the report, per CTEP guidelines.

7.3.3 Expedited Reporting Guidelines

Use the NCI protocol number and the protocol-specific patient ID assigned during trial registration on all reports.

Note: A death on study requires both routine and expedited reporting regardless of causality, unless as noted [below](#). Attribution to treatment or other cause must be

provided.

Death due to progressive disease should be reported as **Grade 5 “Neoplasms benign, malignant and unspecified (incl cysts and polyps) - Other (Progressive Disease)”** under the system organ class (SOC) of the same name. Evidence that the death was a manifestation of underlying disease (e.g., radiological changes suggesting tumor growth or progression: clinical deterioration associated with a disease process) should be submitted.

Late Phase 2 and Phase 3 Studies: Expedited Reporting Requirements for Adverse Events that Occur on Studies under an IND/IDE within 30 Days of the Last Administration of the Investigational Agent/Intervention^{1,2}

FDA REPORTING REQUIREMENTS FOR SERIOUS ADVERSE EVENTS (21 CFR Part 312)

NOTE: Investigators **MUST** immediately report to the sponsor (NCI) **ANY** Serious Adverse Events, whether or not they are considered related to the investigational agent(s)/intervention (21 CFR 312.64)

An adverse event is considered serious if it results in **ANY** of the following outcomes:

- 1) Death
- 2) A life-threatening adverse event
- 3) An adverse event that results in inpatient hospitalization or prolongation of existing hospitalization for ≥ 24 hours
- 4) A persistent or significant incapacity or substantial disruption of the ability to conduct normal life functions
- 5) A congenital anomaly/birth defect.
- 6) Important Medical Events (IME) that may not result in death, be life threatening, or require hospitalization may be considered serious when, based upon medical judgment, they may jeopardize the patient or subject and may require medical or surgical intervention to prevent one of the outcomes listed in this definition. (FDA, 21 CFR 312.32; ICH E2A and ICH E6).

ALL SERIOUS adverse events that meet the above criteria **MUST** be immediately reported to the NCI via CTEP-AERS within the timeframes detailed in the table [below](#).

Hospitalization	Grade 1 Timeframes	Grade 2 Timeframes	Grade 3 Timeframes	Grade 4 & 5 Timeframes
Resulting in Hospitalization ≥ 24 hrs	10 Calendar Days			24-Hour 5 Calendar Days
Not resulting in Hospitalization ≥ 24 hrs	Not required		10 Calendar Days	

NOTE: Protocol specific exceptions to expedited reporting of serious adverse events are found in the Specific Protocol Exceptions to Expedited Reporting (SPEER) portion of the CAEPR

Expedited AE reporting timelines are defined as:

- “24-Hour; 5 Calendar Days” - The AE must initially be reported via CTEP-AERS within 24 hours of learning of the AE, followed by a complete expedited report within 5 calendar days of the initial 24-hour report.
- “10 Calendar Days” - A complete expedited report on the AE must be submitted within 10 calendar days of learning of the AE.

¹Serious adverse events that occur more than 30 days after the last administration of investigational agent/intervention and have an attribution of possible, probable, or definite require reporting as follows:

Expedited 24-hour notification followed by complete report within 5 calendar days for:

- All Grade 4, and Grade 5 AEs

Expedited 10 calendar day reports for:

- Grade 2 adverse events resulting in hospitalization or prolongation of hospitalization
- Grade 3 adverse events

²For studies using PET or SPECT IND agents, the AE reporting period is limited to 10 radioactive half-lives, rounded UP to the nearest whole day, after the agent/intervention was last administered. Footnote “1” above applies after this reporting period.

Effective Date: May 5, 2011

7.3.4 Additional Protocol-Specific Expedited Adverse Event Reporting Exclusions

Not applicable.

7.4 Routine Adverse Event Reporting

All Adverse Events **must** be reported in routine study data submissions. **AEs reported through CTEP-AERS must also be reported in routine study data submissions.**

7.5 Secondary Malignancy

A *secondary malignancy* is a cancer caused by treatment for a previous malignancy (*e.g.*, treatment with investigational agent/intervention, radiation or chemotherapy). A secondary malignancy is not considered a metastasis of the initial neoplasm.

CTEP requires all secondary malignancies that occur following treatment with an agent under an NCI IND/IDE be reported via CTEP-AERS. Three options are available to describe the event:

- Leukemia secondary to oncology chemotherapy (*e.g.*, acute myelocytic leukemia [AML])
- Myelodysplastic syndrome (MDS)
- Treatment-related secondary malignancy

Any malignancy possibly related to cancer treatment (including AML/MDS) should also be reported via the routine reporting mechanisms outlined in each protocol.

7.6 Second Malignancy

A second malignancy is one unrelated to the treatment of a prior malignancy (and is **NOT** a metastasis from the initial malignancy). Second malignancies require **ONLY** routine reporting via CDUS unless otherwise specified.

7.7 Serious Adverse Event (SAE) Reporting for MSK Patients Only

Any SAE must be reported to the IRB/PB as soon as possible but no later than 5 calendar days. The IRB/PB requires a Clinical Research Database (CRDB) SAE report be submitted electronically to

the SAE Office at [contact]. The report should contain the following information:

Fields populated from CRDB:

- Subject's name (generate the report with only initials if it will be sent outside of MSK)
- Medical record number
- Disease/histology (if applicable)
- Protocol number and title

Data needing to be entered:

- The date the adverse event occurred
- The adverse event
- Relationship of the adverse event to the treatment (drug, device, or intervention)
- If the AE was expected
- The severity of the AE
- The intervention
- Detailed text that includes the following
 - An explanation of how the AE was handled
 - A description of the subject's condition
 - Indication if the subject remains on the study
 - If an amendment will need to be made to the protocol and/or consent form.

The PI's signature and the date it was signed are required on the completed report.

8 PHARMACEUTICAL INFORMATION

A list of the adverse events and potential risks associated with the investigational agents administered in this study can be found in [Section 7.1](#).

8.1 CTEP IND Agent(s)

8.1.1 Trametinib dimethyl sulfoxide (GSK1120212B) (NSC 763093) Investigationally labeled

Chemical Name (IUPAC): equimolecular combination of N-(3-{3-cyclopropyl-5-[(2-fluoro-4-iodophenyl)amino]-6,8-dimethyl-2,4,7-trioxo-3,4,6,7-tetrahydropyrido[4,3-d]pyrimidin-1(2H)-yl}phenyl)acetamide with (methylsulfinyl)methane

Other Names: trametinib, GSK1120212, JTP-74057, JTP-78296, JTP-75303, Mekinist

CAS Registry Number: 1187431-43-1

Classification: MEK inhibitor

Molecular Formula: $C_{26}H_{23}FIN_5O_4 \cdot C_2H_6OS$ **M.W.:** 693.54 (dimethyl sulfoxide solvate) 615.41 (anhydrous parent)

Approximate Solubility: Trametinib dimethyl sulfoxide is almost insoluble in water (<0.0001 mg/mL at 25° C)

Mode of Action: Trametinib dimethyl sulfoxide is a reversible, highly selective, allosteric inhibitor of mitogen-activated extracellular signal regulated kinase 1 (MEK1) and MEK2. Tumor cells commonly have hyperactivated extracellular signal-related kinase (ERK) pathways in which MEK is a critical component. Trametinib dimethyl sulfoxide inhibits activation of MEK by RAF kinases and MEK kinases.

Description: Trametinib dimethyl sulfoxide is a white to almost white powder.

How Supplied: GlaxoSmithKline supplies and CTEP, NCI, DCTD distributes 0.5 mg and 2 mg (as free base) tablets. Tablets are packaged in high density polyethylene bottles with child-resistant closures including an induction seal liner. Each bottle contains 32 tablets.

The tablet core contains mannitol, microcrystalline cellulose, hypromellose, croscarmellose sodium, magnesium stearate (non-animal), colloidal silicon dioxide and sodium lauryl sulfate.

- 0.5 mg tablets are yellow, modified oval, biconvex and film-coated. Aqueous film coating consists of Opadry Yellow 03B120006 (hypromellose, titanium dioxide, polyethylene glycol, iron oxide yellow).
- 2 mg tablets are pink, round, biconvex and film-coated. Aqueous film coating consists of Opadry Pink YS-1-14762-A (hypromellose, titanium dioxide, polyethylene glycol, polysorbate 80, iron oxide red).

Storage: Store tablets at 2°C -8°C in the original bottle. Do not repackage tablets or remove desiccant. Bottles should be protected from light and moisture.

Stability: Shelf life studies of trametinib dimethyl sulfoxide are ongoing.

Route of Administration: Oral. Take by mouth on an empty stomach, either 1 hour before or 2 hours after a meal.

Potential Drug Interactions: *In vitro* studies suggest that trametinib dimethyl sulfoxide is not a substrate of CYP enzymes or of human Pgp, BCRP, OATP1B1 or OATP1B3 transporters.

Trametinib dimethyl sulfoxide is a weak CYP2C8 inhibitor and weak CYP3A4 inducer. Drug-drug interactions with sensitive substrates of 2C8 and 3A4 are not anticipated

Availability: Trametinib dimethyl sulfoxide (GSK1120212B) is an investigational agent supplied to investigators by the Division of Cancer Treatment and Diagnosis (DCTD), NCI.

Trametinib dimethyl sulfoxide (GSK1120212B) is provided to the NCI under a Collaborative Agreement between the Pharmaceutical Collaborator and the DCTD, NCI (see [Section 12.3](#)).

8.1.2 Trametinib dimethyl sulfoxide (GSK1120212B) (NSC 763093) Commercially labeled.

Chemical Name (IUPAC): equimolecular combination of acetamide, N-[3-[3-cyclopropyl-5-[(2-fluoro-4-iodophenyl)amino]-3,4,6,7-tetrahydro-6,8-dimethyl-2,4,7-trioxopyrido[4,3-d]pyrimidin-1(2H)-yl]phenyl] with 1,1'-sulfinylbis[methane]

Other Names: trametinib, GSK1120212, JTP-74057, JTP-78296, JTP-75303, Mekinist

CAS Registry Number: 1187431-43-1

Classification: MEK inhibitor

Molecular Formula: $C_{26}H_{23}FIN_5O_4 \cdot C_2H_6OS$ **M.W.:** 693.53

Approximate Solubility: Trametinib dimethyl sulfoxide is almost insoluble in water (<0.0001 mg/mL at 25° C)

Mode of Action: Trametinib dimethyl sulfoxide is a reversible, highly selective, allosteric inhibitor of mitogen-activated extracellular signal regulated kinase 1 (MEK1) and MEK2. Tumor cells commonly have hyperactivated extracellular signal-related kinase (ERK) pathways in which MEK is a critical component. Trametinib dimethyl sulfoxide inhibits activation of MEK by RAF kinases and MEK kinases.

Description: Trametinib dimethyl sulfoxide is a white to almost white powder.

How Supplied: Novartis supplies and CTEP, NCI, DCTD distributes 0.5 mg and 2 mg (as free base) tablets. Each commercially-labeled bottle contains 30 tablets with a desiccant.

The tablet core contains mannitol, microcrystalline cellulose, hypromellose, croscarmellose sodium, magnesium stearate (non-animal), colloidal silicon dioxide and sodium lauryl sulfate.

- 0.5 mg tablets are yellow, modified oval, biconvex and film-coated with 'GS' debossed on one face and 'TFC' on the opposing face. Aqueous film coating consists of hypromellose, titanium dioxide, polyethylene glycol, iron oxide yellow.
- 2 mg tablets are pink, round, biconvex and film-coated with 'GS' debossed on one face and 'HMJ' on the opposing face. Aqueous film coating consists of hypromellose, titanium dioxide, polyethylene glycol, polysorbate 80, iron oxide red.

Storage: Store tablets at 2°C -8°C in the original bottle. Do not repackage tablets or remove desiccant.

Bottles should be protected from light and moisture.

If a storage temperature excursion is identified, promptly return trametinib to 2°C -8°C and quarantine the supplies. Provide a detailed report of the excursion (including documentation of temperature monitoring and duration of the excursion) to [contact] for determination of suitability.

Stability: Refer to the package label for expiration.

Route of Administration: Oral. Take by mouth on an empty stomach, either 1 hour before or 2 hours after a meal. If a dose of trametinib is missed, the dose can be taken if it is more than 12 hours until the next scheduled dose.

Potential Drug Interactions: *In vitro* studies suggest that trametinib dimethyl sulfoxide is not a substrate of CYP enzymes or of human BCRP, MRP2, OATP1B1, OATP1B3, OATP2B1, OCT1 or MATE1 transporters. Trametinib elimination by deacetylation to metabolite M5 is dependent on carboxylesterases (CES1b, CES1c and CES2). M5 is eliminated by CYP3A4 and other pathways, presenting the clinically relevant, albeit low, potential for drug-drug interaction. Trametinib is a substrate for P-gp and BSEP, but this is not expected to be clinically relevant due to trametinib's high permeability.

Trametinib dimethyl sulfoxide is an *in vitro* inhibitor of CYP 2C8, and is anticipated to have overall low potential for drug interactions as a perpetrator. It is also a weak CYP3A4 inducer and expected to have little clinical effect on sensitive substrates. Trametinib is not an inhibitor of CYP 1A2, 2A6, 2B6, 2C9, 2C19, 2D6 and 3A4 and not an inhibitor of P-gp, BCRP, OATP1B1, OATP1B3, OAT1, OAT3, OCT2 MRP2 and MATE1.

Patient Care Implications: Advise women study participants of reproductive potential to use effective contraception while receiving study treatment and for 4 months after the last dose of trametinib. Refer to the protocol document for specific guidance.

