In the phase 3 trial of trametinib vs. chemotherapy in patients with melanoma (MEK114267), cardiomyopathy (defined as cardiac failure, left ventricular dysfunction, or decreased LVEF) occurred in 7% (14/211) of patients treated with trametinib, and in no patients in the chemotherapy arm. Cardiomyopathy was identified within the first month of treatment in five of these 14 patients; median onset of cardiomyopathy was 63 days (range: 16 to 156 days). Cardiomyopathy resolved in 10 of these 14 (71%) patients. Cardiac monitoring should be included in trametinib protocols, to include LVEF assessment by echocardiogram or MUGA scan at baseline, one month after initiation of trametinib and then at 2- to 3-month intervals while on treatment. Refer to dose modification guidelines for cardiac AEs in the event of LVEF decline or symptomatic cardiac AEs.

- Pneumonitis: At the 2 mg monotherapy dose, 0% to 4% of the subjects in five studies had pneumonitis (Investigator's Brochure, 2013). Of the nine total subjects (including crossovers) experiencing pneumonitis AEs at this dose, three subjects had grade 1 or 2 pneumonitis and six subjects had grade 3 pneumonitis.
- Embryofetal toxicity: Based on its mechanism of action, trametinib can cause

fetal harm when administered to a pregnant woman. Trametinib was embryotoxic and abortifacient in rabbits at doses greater than or equal to those resulting in exposures approximately 0.3 times the human exposure at the recommended clinical dose. If this drug is used during pregnancy, or if the patient becomes pregnant while taking this drug, the patient should be apprised of the potential hazard to a fetus.

Incidence of common AEs reported from a phase III trial of trametinib vs. chemotherapy in patients with advanced melanoma: Patients with abnormal LVEF, history of acute coronary syndrome within 6 months, or current evidence of Class II or greater congestive heart failure (New York Heart Association) were excluded from this trial. Selected adverse reactions (AR) occurring in patients receiving trametinib as compared to patients in the chemotherapy arm are listed as [below](#):

Table: Selected adverse reactions (ARs) occurring in $\geq 10\%$ of patients receiving trametinib AND at a higher incidence than in the chemotherapy arm (high in the trametinib arm compared with chemotherapy by $\geq 5\%$ in overall incidence or by $\geq 2\%$ grade 3 or 4 AEs)

Adverse Reactions	Trametinib (n=211)		Chemotherapy (n=99)	

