AST (SGOT)/ALT(SGPT)	$\leq 1.5 \text{ X}$ institutional upper limit of normal for patients with no concurrent liver metastases, OR $\leq 2.5 \text{ X}$ institutional upper limit of normal for patients with concurrent liver metastases

Creatinine	$\leq 1.5 \text{ mg/dL}$ OR Calculated creatinine clearance (Cockcroft-Gault formula) $\geq 50 \text{ mL/min}$ OR 24-hour urine creatinine clearance $\geq 50 \text{ mL/min}$
------------	--

Left ventricular ejection fraction \geq institutional lower limit of normal (LLN) by ECHO

or MUGA

***Note:** Patients with hyperbilirubinemia clinically consistent with an inherited disorder of bilirubin metabolism (e.g., Gilbert syndrome) will be eligible at the discretion of the treating physician and/or the principal investigator.

3.1.10 The effects of trametinib and GSK2141795 on the developing human fetus are unknown. For this reason, and because MEK inhibitors as well as other therapeutic agents used in this trial are known to be teratogenic, women of child-bearing potential and men must agree to use adequate contraception (hormonal or barrier method of birth control; abstinence) prior to study entry and for the duration of study participation. Women of child-bearing potential must have a negative blood pregnancy test within 14 days prior to start of protocol treatment. Should a woman become pregnant or suspect she is pregnant while she or her partner is participating in this study, she should inform her treating physician immediately. Men treated or enrolled on this protocol must also agree to use adequate contraception prior to the study, for the duration of study participation, and 4 months after completion of trametinib administration.

3.1.11 Ability to understand and the willingness to sign a written informed consent document.

3.1.12 Patients must agree to provide all imaging studies for central radiology review. This central radiology review may be performed retrospectively and will not be utilized for decision making for patients on study.

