- History or evidence of current \geq Class II congestive heart failure as defined by the New York Heart Association (NYHA) functional classification system (see [Appendix C](#)).
- Treatment-refractory hypertension defined as a blood pressure of systolic >140 mmHg and/or diastolic >90 mmHg which cannot be controlled by anti-hypertensive therapy.
- Patients with intra-cardiac defibrillators.
- Known cardiac metastases.

3.2.11 Known Hepatitis B Virus (HBV) or Hepatitis C Virus (HCV) infection (patients with chronic or cleared HBV and HCV infection are eligible). Patients with Human Immunodeficiency Virus (HIV) are not eligible if on anti-retroviral medications.

3.2.12 Uncontrolled intercurrent illness including, but not limited to, ongoing or active infection, symptomatic congestive heart failure, unstable angina pectoris, cardiac arrhythmia, or psychiatric illness/social situations that would limit compliance with study requirements.

3.2.13 Animal reproductive studies have not been conducted with trametinib or GSK2141795. Therefore, the study drug must not be administered to pregnant women or nursing mothers. Women of childbearing potential should be advised to avoid pregnancy and use effective methods of contraception. Men with a female partner of childbearing potential must have either had a prior vasectomy or agree to use effective contraception. If a female patient or a female partner of a patient becomes pregnant while the patient receives trametinib, the potential hazard to the fetus should be explained to the patient and partner (as applicable).

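### Criterion 3.1.10 sets a 4-month contraception period after trametinib for men only and 3.2.13 gives women no duration, while Section 8.1.2 advises 4 months for women; 3.2.13 also misstates the animal data

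*Combined protocol and SAP*

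**What the plan says.** Criterion 3.1.10 has women of child-bearing potential and men agree to adequate contraception "prior to study entry and for the duration of study participation". A later sentence in the same criterion, addressed to men only, repeats the period of study participation and adds "and 4 months after completion of trametinib administration".

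Criterion 3.2.13 states: "Women of childbearing potential should be advised to avoid pregnancy and use effective methods of contraception". It gives no duration. It also states: "Animal reproductive studies have not been conducted with trametinib or GSK2141795".

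Section 8.1.2 (commercially labeled trametinib, Patient Care Implications) tells sites to advise women of reproductive potential to "use effective contraception while receiving study treatment and for 4 months after the last dose of trametinib", followed by "Refer to the protocol document for specific guidance". Section 8.1.1, on investigationally labeled trametinib, has no contraception advice.

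Section 2.2.1.3 says that trametinib can cause "fetal harm when administered to a pregnant woman". It also reports animal data: "Trametinib was embryotoxic and abortifacient in rabbits at doses greater than or equal to" those giving about 0.3 times the human exposure at the recommended dose.

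**The concern.** The agreement that a woman makes at entry is the one in 3.1.10, and a site reading that criterion finds a post-treatment period for men alone. The only text that gives women a period is in the monograph for one of the two trametinib supplies, and it refers back to a protocol whose criteria do not contain the period. A site that follows 3.1.10 as written could therefore apply a shorter safeguard than the document itself advises, for a drug that it says can harm a fetus.

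The animal-study sentence in 3.2.13 adds to this. For trametinib it understates what the background section reports, and it does so in the criterion meant to prevent exposure in pregnancy.

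**Working it through.** The protocol states no figure to reproduce here. The main check sets the texts side by side; the arithmetic only sizes the gap.

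**Contraception period after the last trametinib dose, by place**

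| Place | Women | Men |
|---|---|---|
| 3.1.10 | none stated beyond study participation | 4 months |
| 3.2.13 | no duration | no duration |
| 8.1.1 (investigational label) | no advice | no advice |
| 8.1.2 (commercial label) | 4 months | not mentioned |

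No other section of the available text gives women a post-treatment period.

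**Length of the advised period.** Take a last dose on 31 March 2017, the date by which Section 5.1 requires all patients to be off treatment. Four calendar months run to 31 July 2017: 30 + 31 + 30 + 31 = 122 days, and 122 / 7 = 17.4 weeks.

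**Share not covered for women in 3.1.10.** The answer turns on when study participation ends, so three readings are shown:

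- It ends at removal from study. Under Sections 5.3 and 5.5 the reasons for stopping treatment are also the reasons for removal, so this is taken as the last dose: 122 / 122 = 100%.
- It ends at the End of Treatment visit, 4 weeks after the last dose (Section 10, note n; Section 5.4 also gives 4 weeks): 122 − 28 = 94 days, or 13.4 weeks; 94 / 122 = 77%.
- It includes survival follow-up (Section 5.4), assuming that this continues through the 4 months: 0 / 122 = 0%.

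**Which reading is natural.** The men's sentence names study participation and then lists the 4 months as something further. If participation already included survival follow-up, the addition would usually be redundant. This favors the first two readings without excluding the third.

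**Drug remaining.** Section 2.2.1.2 gives an effective half-life of about 4.5 days. By day 28, 28 / 4.5 = 6.2 half-lives have passed, and 2^(−6.2) = 1.3% remains, if a single half-life describes elimination. The uncovered days therefore measure distance from the document's own advice, not drug exposure.

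**Number of women.** Section 3.4 plans 40 women among 80 patients. Section 13.2 gives up to 60 patients; with the same split, 60 × 40 / 80 = 30. So 30 to 40 women would be expected over the whole trial. No count of those of child-bearing potential, or of those still on treatment, is given. Section 2.1 gives a median age at diagnosis of 62.

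**Animal studies.** The sentence in 3.2.13 covers trametinib and GSK2141795 together. For trametinib, the rabbit findings in 2.2.1.3 contradict it. Nothing in the available text contradicts it for GSK2141795.

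**The case against.** The strongest reply is that the advice already exists: 8.1.2 is an instruction to counsel women for 4 months, so what remains is alignment between sections. That stands. A reader might infer that women get no post-treatment advice at all; 8.1.2 rules that out, and the consent form, which is not available here, may also state the period. What the reply does not remove is that the advice is attached to one labeled supply and points back to criteria that lack it.

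A second reply is that study participation can be read broadly. The men's 4 months run from completion of trametinib, not from the end of participation, so the two periods may overlap and the men's wording does not settle the meaning. This also stands. It is why the gap is given as a range, and why 77% should not be quoted alone.

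A reader might further infer that the End of Treatment visit is the last scheduled contact at which the advice is still useful. The documents do not support that:

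- Section 10, note g, keeps patients who stop without progression on scans every 8 weeks (± 1) until progression, new anticancer therapy or death. About two scans would fall within 17.4 weeks for a patient who stays on that schedule.
- Section 5.4 follows patients removed for adverse events until resolution or stabilization.
- Survival contact is not fixed late in the period. Counted from a 4-week visit, it falls at weeks 15 to 17 (15 / 17.4 = 86% to 17 / 17.4 = 98% of the period). Note n also lets contact run from the last date of follow-up, and lets the last treatment visit stand in when a patient cannot return. Counted from the last dose, contact falls at weeks 11 to 13 (63% to 75%).

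Finally, 3.2.13 still bars treatment of pregnant and nursing women, and 3.1.10 already describes MEK inhibitors as teratogenic. The misstated animal data therefore remove no protection, though the sentence is still wrong for trametinib.

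**Conclusion.** The inconsistency is real and can be read directly from the text. In the eligibility criteria, men have a 4-month period after trametinib and women have none, while 8.1.2 advises 4 months for women. The uncovered share for women is about 100%, 77% or 0%, depending on an undefined term; the 0% reading is possible but less natural. The animal-study sentence in 3.2.13 is contradicted for trametinib by Section 2.2.1.3.

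The practical effect is probably small: few women are likely to be of child-bearing potential, and little drug should remain after 4 weeks under the half-life assumption. The potential harm is serious and the correction cheap, so it is worth making. This is a participant-safety wording point of minor priority, with no bearing on the endpoint, power or analysis.

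**What to change.** 1. Now, without an amendment, because 8.1.2 already directs it: give the 4-month advice to every woman of child-bearing potential on treatment, whichever trametinib supply she receives.
2. In the next amendment: extend the commitment for women in 3.1.10 to 4 months beyond the final trametinib dose, state the same period in 3.2.13, and correct the animal-study sentence there for trametinib.
3. Align the consent form if it does not already state the period.

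For participants, the cost is a slightly longer contraception commitment for what is probably a small number of women. For the trial, the cost is approval by the MSK IRB/PB and the site IRBs. Under Section 12.1.2 (Amendments), a safety-driven or more restrictive change stops new enrolment at a site until its IRB approves, and sites have up to 90 days. From the current version date, 1 December 2016, to 31 March 2017 is 120 days, so a site using all 90 would have at most 120 − 90 = 30 days left, and the amended entry criterion would then reach few new patients. Folding the text change into another amendment limits the cost, and step 1 does not wait for it.
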